## **Sponsor**

Bournemouth University

## **Funder**

Bournemouth University  
 Poole Hospital NHS Foundation Trust

## Amendment History

Amendment No.	Protocol Version No.	Date issued	Author(s) of changes	Details of Changes made

## Study synopsis

Study title	Shared decision-making: investigating the potential of an interactive, web-based information tool to support treatment choice of people with advanced pancreatic cancer
Sponsor Reference No.	
Study design	Multiphase mixed methods design
Study participants	Oncologists, clinical nurse specialists, people diagnosed with advanced pancreatic cancer, and their relatives who provide care and support for them
Sample size	120
Follow-up duration	Not applicable
Planned study period	August 2018 – December 2019
Primary objectives	To investigate the potential of a web-based, interactive, information tool in facilitating shared decision-making for the choice of treatment for people with advanced pancreatic cancer (APC)
Secondary objectives	
 
(i) To assess the quality of life, efficacy, and safety of chemotherapy treatments of APC through systematic review and network meta-analysis (NMA) of randomized controlled trials (RCTs).
 
(ii) To explore the expectations and preferences of clinicians, people with APC, and their relatives, when making decisions about treatment, through focus groups and semi-structured interviews for clinicians, and people with APC (including their relatives), respectively.
 
(iii) To identify the features necessary for the design of a web-based information tool to facilitate SDM between clinicians and people with APC about choice of treatment.
 
(iv) To evaluate the effectiveness of the developed information tool in SDM, through a pilot test with clinicians (doctors and nurse specialists), people with APC, and their relatives.
 

Primary endpoint	Effectiveness of Shared decision-making
Interventions	Not applicable

## Abbreviations

AE	Adverse Event
BSC	Best Supportive Care
BU	Bournemouth University
BUCRU PPI	Bournemouth University Clinical Research Unit Patient and Public Involvement
CI	Chief Investigator
DCS	Decisional Conflict Scale
EU	European Union
HRQoL	Health Related Quality of Life
MRC	Medical Research Council
NHS	National Health Service
NMA	Network Meta-analysis
PC	Pancreatic Cancer
PCUK	Pancreatic Cancer United Kingdom
PIS	Participant Information Sheet
R&KEO	Research & Knowledge Exchange Office
RCT	Randomised Controlled Trial
REC	Research Ethics Committee
SDM	Shared Decision Making
SUCRA	Surface Under the Cumulative Rank Area
SUS	System Usability Scale

### Key Words

Pancreatic cancer, web-based information tool, patient decision aid, mixed methods, systematic review, network meta-analysis, interviews, focus group

# 1 Introduction

## 1.1 Background

Pancreatic cancer (PC) is a disease with very low 5-year survival rates. Some estimates set this at less than 5% (Vincent et al. 2011; Balaban et al. 2016). In the European Union (EU), over 85,000 deaths were projected in 2017, which is a rise of around 8.0% from 2012 (Malvezzi et al. 2017). PC can be broadly classified as locally resectable, borderline resectable, locally advanced, and metastatic (Vincent et al. 2011). Treatments include surgery, chemotherapy, radiation therapy, and palliative care (Kamisawa et al. 2016). Surgery offers curative treatment, but 80% of patients are diagnosed in the advanced stage (locally advanced or metastatic) and are ineligible (Ducréux et al. 2015; Taieb et al. 2017). However, systemic therapy (such as chemotherapy) is a palliative option for people with advanced pancreatic cancer (APC) (Balaban et al. 2016). “Best supportive care” (BSC), or “supportive care”, is another option which involves symptom management and improving quality of life (Hui et al. 2013).

Shared decision-making (SDM) is a process where clinicians and patients make decisions together using the best available evidence (Elwyn et al. 2010). SDM is recognised as a policy priority and ethical imperative by the National Health Service (NHS) and several healthcare regulators in the United Kingdom (UK), respectively (Coulter et al. 2017). The concept of equipoise is a scenario where there is more than one legitimate choice of treatment for a medical condition (Edwards et al. 2000; Elwyn et al. 2000). It offers an opportunity to apply SDM in discussing the choice of treatment for people with APC because there is no clear preference of treatment options in terms of benefits and risks for APC (Balaban et al. 2016). Moreover, a systematic review by Gravel et al. (2006) indicated, among other things, that SDM facilitated positive impact on the clinical process and patient outcomes. Encouraging SDM in APC treatment could yield similar results, including the reduction in selecting aggressive treatments that have little or no corresponding economic or personal benefits (Oshima Lee and Emanuel 2013; Veroff et al. 2013).

Several tools have been developed to enhance SDM in relation to other medical conditions (Agoritsas et al. 2015; Elwyn et al. 2016). Some of these tools are for ovarian cancer (Vogel et al. 2013), stage IV lung cancer (Leighl et al. 2008), and colorectal cancer (Leighl et al. 2011). CONNECT™ is a computer-based tool that was developed for the general improvement of the doctor-patient communication process (Meropol et al. 2013). Additionally, a systematic review conducted by Austin et al. (2015) showed that decision tools can improve patients’ knowledge and awareness of the treatment options available to them. However, there is very little in literature about the use of evidence-based digital tools in discussing the expected outcomes of treatment for people with APC. Although predictive tools have been developed for PC (Ansari et al. 2013; Smith and Mezher 2014; Walczak and Velanovich 2017), there is currently no web-based information tool that can provide clinical evidence on the treatment choices available to people with APC.

However, there is an online decision aid developed for patients with APC in Canada (Gresham 2013). It has some useful features which can help its users make decisions about their treatment, including information about APC. However, its automation in comparing treatment options is basic, its depth of information necessary for decision-making, and its flexibility could be improved. Its target audience are the patients only. It also assumes that users typically have only 3 options to choose from.

It is necessary that patients are fully aware of the benefits and risks associated with any treatment that is being proposed to them. Also, to ensure that clinicians provide the best available evidence-based information in an easily understandable format for the patients, the purpose of this study is to develop an interactive, web-based

information tool to assist in the process of shared decision-making between clinicians, and patients and their relatives (or caregivers).

## **1.2 Research rationale**

### **1.2.1 The need for an evidence-based information tool for APC treatment options**

There is currently no web-based, SDM tool for APC that presents information on available treatment options in a visual, and concise way to patients so that they and their clinicians can make informed choices. Acceptability and reliability are two important factors to be considered when developing such tools (Coulter et al. 2017).

### **1.2.2 The support for the policy priority for patient-centred care in the UK**

In the United Kingdom, shared decision-making is viewed as a priority in patient care (Coulter et al. 2017). However, effective SDM is enhanced through well-informed participants, and that is an objective of the proposed information tool.

### **1.2.3 Enhancing clinicians' communicative skills**

Geessink et al. (2017) identified communicative skills in healthcare professionals as a requisite for successful SDM. The proposed information tool is hoped to enhance clinicians' capacity to communicate available treatment options with their patients by presenting pertinent facts in a concise and user-friendly manner for them.

### **1.2.4 Improving medical cost-effectiveness**

This tool could also potentially challenge the “more-is-better” attitude (assumption that expensive treatment equals better healthcare) held by the public (Levinson et al. 2015). Evaluation of some patient decision aids showed improved cost-effectiveness in some medical conditions (O'Connor et al. 2004). Introducing the information tool to APC treatment could potentially yield similar results.

## **2 Objectives**

### **2.1 Primary objective**

To investigate the potential of a web-based, interactive, information tool in facilitating shared decision-making in the choice of treatment for people with advanced pancreatic cancer

### **2.2 Second objectives**

- (i) To assess the quality of life, efficacy, and safety of chemotherapy treatments of APC through systematic review and network meta-analysis (NMA) of randomized controlled trials (RCTs).
- (ii) To explore the expectations and preferences of clinicians, people with APC, and their relatives, when making decisions about treatment, through focus groups and semi-structured interviews for clinicians, and people with APC (including their relatives), respectively.
- (iii) To identify the features necessary for the design of a web-based information tool to facilitate SDM between clinicians and people with APC about choice of treatment.
- (iv) To evaluate the effectiveness of the developed information tool in SDM, through a pilot test with clinicians (doctors and nurse specialists), people with APC, and their relatives.

### 3 Study design

A multiphase mixed methods research design has been adopted for this study. It involves a series of either sequential or concurrent discrete phases (Creswell 2010, p.100). This design was chosen because of the nature of the research questions that are both qualitative and quantitative, and because multiphase mixed methods is suitable for evaluation of intervention programs (Creswell 2014). This project involves evaluation of an information tool.

**Error! Reference source not found.** is an overview of the research design. Phases 1 and 2 will occur concurrently and will generate information required for the tool development in phase 3. Finally, Phase 4 will test the developed tool. The next section (Research methods) describes these phases in detail.

[figure not shown]

Figure 1: Study Design Diagram

#### 3.1 Research methods

##### 3.1.1 Phase 1: Systematic review and network meta-analysis

A systematic review and network meta-analysis (SR & NMA) of clinical trials in APC treatment shall be performed. The aim is to assess the comparative efficacy and safety of the different chemotherapy treatments for APC from reported randomised controlled trials. This will provide a basis for the design of the information tool. Network meta-analysis is chosen because it has the capacity to make comparison between treatments in different studies when they have a common-comparator treatment (Jones et al. 2011; Catala-Lopez et al. 2014). Traditional meta-analysis summarizes treatment effects for similar studies that compare the same kind of regimens, however network meta-analysis is designed to summarize and compare effects of different studies. For example, if study 1 compares treatment A vs. B, and study 2 compares treatment B vs. C, there is a common comparator, treatment B, between studies 1 and 2. Using network meta-analysis, it is statistically possible to compare the effects of treatment C vs. A, even if they were never compared in an actual study (Zocca 2014, p.27), provided that these studies exhibit the transitivity assumption, that is, they are similar in all respects (Salanti et al. 2014). The outcome of this network meta-analysis shall be a probability ranking of different available treatment options based on a chosen endpoint (study outcome), and surface under the cumulative area (SUCRA) statistic (Salanti et al. 2011). The endpoints chosen for this network meta-analysis are: overall survival, progression-free survival, disease

control rate, toxicity (neutropenia, leukopenia, thrombocytopenia, nausea, fatigue), and health-related quality of life (HRQoL).

The eligibility criteria of included studies for the SR & NMA are:

- i. First-line chemotherapy treatment. These are treatments used as the primary or initial treatment
- ii. Phase III randomised controlled trials. These are trials designed for actual participants from the target population to determine drug effect
- iii. Locally advanced or metastatic PC
- iv. Full-text articles
- v. English version of reported trials
- vi. Studies considering Best Supportive Care (BSC) will be included. These kinds of studies typically compare a regimen against symptom management.
- vii. Studies published from 1997 onwards; this criteria was chosen because of a landmark study (Burris et al. 1997) that established a chemotherapy treatment standard for APC.

Databases to be searched include PubMed, MEDLINE, EMBASE, CENTRAL, Web of Science, and Scopus. Manual search of article references will also be done.

### **3.1.2 Phase 2a: Focus groups/interviews with clinicians**

Focus groups (or semi-structured interviews) will be conducted for clinicians (doctors and clinical nurse specialists) involved in cancer treatment. The focus groups (or personal interviews if more convenient for the participants) will be done to explore the experiences of the participants in discussing treatment options with patients before commencement of treatment. The potential use of an information tool for SDM will be explored during the discussions. It is anticipated that an observer who is a member of the supervisory team (or somebody nominated by them) will assist the postgraduate researcher during the conduct of the focus groups.

The venue for the focus groups (or semi-structured interviews) will be at the hospitals. The maximum duration is 1 hour.

### **3.1.3 Phase 2b: Interviews with patients and relatives**

Patients and their relatives shall be interviewed separately to elicit their experiences about the consultations they had with clinicians, their mode of information access regarding pancreatic cancer, and what they felt could have helped them in making choices. Preferences about quality-of-life issues, information needs, and attitudes about the use of a web-based tool shall be explored.

The venue for each interview will be at the hospital, or by phone, or via Skype (or any appropriate teleconferencing application). For patients and relatives, there is an option of conducting the interview at the residence of the participants (or other convenient locations).

All focus groups and interviews will be audio-recorded (with permission of participants) for transcription purposes.

### **3.1.4 Phase 3: Information tool development**

A web-based information tool shall be designed using an appropriate technology. Shiny package for R^1, or Java Enterprise Edition 2 are being considered for this phase. A human-centred approach (Giacomin 2014) will be adopted in reasoning about the information tool development. It involves communicating with the intended users and understanding their needs, experiences and incorporating feedback into the development process.

---

 <https://shiny.rstudio.com/>

 <http://www.oracle.com/technetwork/java/javaee/overview/index.html>

The information tool shall incorporate data from the SR & NMA, and from the qualitative data analysis from phase 2. Its essential functionalities will include the ability to display the available treatment options to users based on selected outcomes, while comparing the benefits and risks of each option.

The web-based tool will be hosted on BU web development server.

### **3.1.5 Phase 4: Evaluation of developed information tool**

The resulting web-based information tool will be tested for its functionality, usability, and effectiveness in SDM. Target users are clinicians, patients and relatives of patients. Users will be asked to perform certain tasks with the developed tool. These tasks will be based on the expected functionalities of the proposed information tool. Phase 2 will elicit some of the requirements and functionalities of the proposed information tool.

Phase 4 is designed to be accomplished in two stages:

Stage 1 will assess the information tool's usability. It will be for participants who were involved in the study during the focus group or semi-structured interviews (phase 2). Participants will be asked to complete predefined tasks using the information tool. Participants will then provide feedback to inform the tool modification. There will be options to accomplish the tasks from the residence of participants through web links to the information tool and an online feedback form. Feedback is in the form of a questionnaire and open-ended questions.

Data from stage 1 is primarily for refining the information tool's functionality and usability in preparation for stage 2.

The average duration for stage 1 test is 30 minutes.

Stage 2 will evaluate the effectiveness of the proposed information tool in the SDM process. It is targeted at real-life consultations between clinicians and patients who are starting consultations about their treatment. These patients and relatives will be recruited for this stage. Evaluation at this stage involves the effectiveness of the decision-making process and decision quality (Sepucha et al. 2013) of the information tool.

Effectiveness of the decision-making process is the extent to which the information tool helps the participants in the SDM process. However, decision quality or quality of choice measures the extent to which patients are fully informed and receive the treatments consistent with their preferences (Sepucha et al. 2013).

A variety of instruments have been proposed for measuring the effectiveness of SDM process (Scholl et al. 2011) and the effectiveness of decision aids (Sepucha et al. 2013). The Decision Conflict Scale (DCS) (O'Connor 1995) will be adopted for this purpose because it has been validated in many studies, it has more than one version to suit different participants (Légaré et al. 2012), and it is freely available.

After each consultation involving SDM with the information tool, all participating parties (clinician, patient, relative) will fill out the appropriate DCS form. The form is to be completed and returned within 4 weeks after consultation. This is to enable the participants to give a reliable evaluation of their experience during the consultation.

The instruments can be returned at the hospital, by email, or post (stamped addressed envelopes will be provided).

Electronic versions of the DCS will be developed and interested participants can choose to provide feedback through this option.

The duration for filling the DCS form is approximately 10 minutes.

To assess the decision quality associated with the information tool, Sepucha et al. (2013) noted that more than half of the tools reported in the literature were original products designed to meet the requirements of each study. Consequently, the development of a customised instrument to assess the quality of the decision associated with the proposed information tool may be explored. As in the case of breast cancer decision quality measurement (Sepucha et al. 2007; Lee et al. 2010), the major contents of the decision quality instrument for APC treatment will be

disease-specific knowledge and value items or goals of the treatment for people with APC.

The content of the proposed instrument will require about 10 minutes to complete.

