### **3.2 Study Primary and secondary outcome measures**

The second phase of the study is a qualitative study that includes interviews and focus groups. Factors that influence the decision-making process during choice of PC treatment, and information needs of these groups of people will be explored. For the test/evaluation phase of the study, the primary outcome measures are the decisional conflict and system usability score. These will be measured with the DCS and (adaptions of) the System Usability Scale (SUS) (Brooke 1996), respectively.

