#### **5.2 Treatment Arms**

This is a single arm study.

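### The Stage 2 aim is to show how far the tool helps, but a single-arm DCS taken only after tool-supported consultations describes decisional conflict and does not isolate the tool's contribution

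*Protocol*

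**What the plan says.** Protocol section 3.1.5 states the purpose of the second evaluation stage: "Stage 2 will evaluate the effectiveness of the proposed information tool in the SDM process". It then gives the term a meaning: "Effectiveness of the decision-making process is the extent to which the information tool helps the participants in the SDM process". The DCS is chosen to measure this; it "will be adopted for this purpose because it has been validated in many studies". Secondary objective (iv) in section 2.2, also in the synopsis, carries the same aim: "To evaluate the effectiveness of the developed information tool in SDM, through a pilot test".

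The data collection is described in the same section: "After each consultation involving SDM with the information tool, all participating parties (clinician, patient, relative) will fill out the appropriate DCS form". Forms may be completed and returned up to 4 weeks later. Section 8.2 again places data collection after the consultation and says that Stage 2 patients and relatives will be people not previously in the study. Section 5.2 states: "This is a single arm study".

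Other parts are more modest. The primary objective (section 2.1) is to investigate the tool's potential. Section 8.1 plans descriptive statistics for Phase 4 and refers to the DCS user manual for details. Section 3.2 says that, for the evaluation phase, "the primary outcome measures are the decisional conflict and system usability score". The synopsis names the primary endpoint as "Effectiveness of Shared decision-making", a phrase that the protocol does not define.

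**The concern.** How far a tool helps is a contrast: decision-making with the tool against decision-making without it. Stage 2 observes only the first half. A DCS score after the consultation reflects the tool, the consultation itself, the uncertainty that the patient or relative brought to it, and anything that happens before the form is filled in.

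The stake is the conclusion that may be drawn. Taken at its word, section 3.1.5 invites a report that the tool was effective, based on scores that could equally have arisen without it. The tool is meant for people with advanced pancreatic cancer who are choosing treatment, so that conclusion should not go beyond the data.

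**Working it through.** **The plan's own figure.** Section 8.2 takes a recommended 20 to 25 for a single group and raises it to 30 tests for incomplete or missing questionnaires. No loss rate is stated. Solving 30 = N/(1 − d) for d:

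- N = 25: d = 1 − 25/30 = 16.7%
- N = 20: d = 1 − 20/30 = 33.3%

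The 30 is arithmetically plausible and is not disputed here. It does not bear on the main point.

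**Aim against data.**

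- Aim (sections 3.1.5 and 2.2): effectiveness of the tool, understood in 3.1.5 as the extent of its help.
- Instrument (3.1.5): DCS.
- Timing (3.1.5 and 8.2): after the tool-supported consultation only.
- Comparator (5.2 and 4.3): one arm and no randomisation.
- Earlier scores on the same people (8.2): none available, since Stage 2 patients and relatives are new to the study.
- Analysis (8.1): descriptive statistics.

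The text shown contains no pre-consultation DCS and no concurrent comparator. Figure 3, the second-stage flow, is not shown, but sections 3.1.5 and 8.2 are explicit that collection follows the consultation.

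**What the data can estimate.** Tool contribution = mean DCS with the tool − mean DCS without it. Only the first term is observed. For illustration, assume an observed mean of 30 and that higher scores mean more conflict (neither figure nor direction is given in the protocol):

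- unmeasured no-tool mean 40: 30 − 40 = −10 (tool reduced conflict)
- unmeasured no-tool mean 30: 30 − 30 = 0 (no effect)
- unmeasured no-tool mean 20: 30 − 20 = +10 (tool increased conflict)

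The same observed mean fits all three. More participants would make the 30 more precise and leave the second term unknown.

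**Stage 2 number, a separate inconsistency within section 8.2.**

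- Table 2: 20 to 30 patients plus 5 to 15 relatives, so 20 + 5 = 25 to 30 + 15 = 45.
- Text on sample size: 30 tests. In Stage 1 a test is counted per participant (5 + 5 + 5 = 15); for Stage 2 the unit is not stated.
- Closing paragraph: about 20 to 30 participants, patients and relatives together.

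The first and third readings overlap only from 25 to 30, and their upper ends differ by 45 − 30 = 15 people.

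**The case against.** The strongest reply is that the protocol already describes an uncontrolled descriptive pilot. The primary objective speaks only of potential, objective (iv) is secondary and says it is a pilot test, the sample size is framed for a single group, and no test, comparison or causal statement is planned. All of this stands. It limits the problem to the aim and definition in section 3.1.5 and, more weakly, to objective (iv). It does not remove it, because section 3.1.5 ties effectiveness to the tool's help and assigns the DCS to measure that.

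A reader might infer that the primary endpoint itself calls for a conclusion about the tool's effect. The documents do not support this. The synopsis wording names shared decision-making, not the tool, and section 3.2 gives the outcomes as DCS and usability. The endpoint is undefined and out of line with section 3.2, which is a lesser fault.

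A reader might also infer that no analysis could ever supply a contrast. That goes too far. An analysis plan could set the scores against an external reference value, and the absence of one from the protocol is no fault. Such a contrast would be weak and confounded, since it would compare different people in different consultations.

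**Conclusion.** The point holds in a limited form. Section 3.1.5 claims a property that the Stage 2 design lacks: a post-consultation DCS in one arm does not isolate how far the tool helped. The section 3.2 outcomes and the descriptive statistics in section 8.1 can be delivered as planned.

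The defect has no numerical size. It concerns what is identified and not precision, so a confidence interval width would not measure it. The conclusion rests on the text shown, with Figure 3 and the DCS user manual not at hand. A cut-off in that manual, if there is one, could classify the scores but would not show what the tool changed.

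It would be wrong to read this as a case for a control arm or a mandatory baseline. A single-arm pilot is legitimate when its stated aim matches what it can show.

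**What to change.** - **Section 3.1.5 and objective (iv) (section 2.2 and synopsis):** restate the Stage 2 aim as describing decisional conflict (DCS), and decision quality if that instrument is used, after tool-supported consultations in an uncontrolled pilot. Replace the definition that rests on the tool's help. State that no conclusion that the tool caused the result will be drawn.
- **Usability:** keep it under Stage 1, where section 3.1.5 places it.
- **Synopsis:** reword the primary endpoint to the section 3.2 outcomes, DCS and the System Usability Scale.
- **Section 8.2:** separately, settle whether 20 to 30 means patients alone or patients and relatives together, and say what one of the 30 tests is.

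The cost is wording only, with no extra participants, data or burden.

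A pre-consultation DCS is not required. It would show change around the consultation and would still not separate the tool from the consultation. It would also use up the questionnaire time: 10 + 10 = 20 minutes, the limit in section 7.3, or 10 + 10 + 10 = 30 minutes if the decision-quality form is also used.
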